5.5.2.3 Medical History

Partially missing diagnosis dates will not be imputed.

5.5.2.4 Concomitant Medications

Missing concomitant medication dates will be handled in a similar fashion as described for Adverse Events in Section 5.5.2.1.

5.6 Windowing Conventions

For safety data which are not linked to nominal visits (e.g. AEs) as per the protocol schedule of assessments, these data will be mapped to the cycle of treatment in which they onset according to Table 10 and Table 11.

For safety data collected at nominal visits, the recorded nominal visit will be used and unscheduled visits will be mapped to the nearest planned visit where it would be expected to be recorded, by study visit day, as per the protocol. If a record is mapped to a visit which has a valid reading nominally assigned, the nominally assigned visit value will be used in all summaries and analysis.

Table 10: Visit Windows – Treatment Phase

Assessment Study Day	Visit	Visit Label	Study Visit Day
	Screening	Screening	-45
2≤Sday<8	Cycle 1 – Week 1 (Baseline, study visit day 1)	C1D1	1
8≤Sday<29	Cycle 1 - Week 3 (Cycle Day 15)	C1D15	15
29≤SDay<57	Cycle 2 - Week 7 (Cycle Day 15)	C2D15	43
57≤SDay<85	Cycle 3 - Week 11 (Cycle Day 15)	C3D15	71
85≤SDay<113	Cycle 4 – Week 15 (Cycle Day 15)	C4D15	99
113≤SDay<141	Cycle 5 - Week 19 (Cycle Day 15)	C5D15	127
141≤SDay<169	Cycle 6 - Week 23 (Cycle Day 15)	C6D15	155
169≤SDay<197	Cycle 7 - Week 27 (Cycle Day 15)	C7D15	183
197≤SDay<225	Cycle 8 - Week 31 (Cycle Day 15)	C8D15	211
225≤SDay<253	Cycle 9 - Week 35 (Cycle Day 15)	C9D15	239
253≤SDay<281	Cycle 10 – Week 39 (Cycle Day 15)	C10D15	267
281≤SDay<309	Cycle 11 - Week 43 (Cycle Day 15)	C11D15	295
309≤SDay<337	Cycle 12 - Week 47 (Cycle Day 15)	C12D15	323
337≤SDay<365	Cycle 13 - Week 51 (Cycle Day 15)	C13D15	351
365≤SDay<393	Cycle 14 - Week 55 (Cycle Day 15)	C14D15	379

Document: S:\Q_146\Q_03974\MEK-NF-201\Prog_Stat\Documentation\SAP\MEK-NF-201 SAP v1.0.0.docx

Author:

	Safety Follow-up = 30 days after last dose	SFU	-
645≤SDay<673	Cycle 24 - Week 95 (Cycle Day 15)	C24D15	659
617≤SDay<645	Cycle 23 – Week 91 (Cycle Day 15)	C23D15	631
589≤SDay<617	Cycle 22 - Week 87 (Cycle Day 15)	C22D15	603
561≤SDay<589	Cycle 21 – Week 83 (Cycle Day 15)	C21D15	575
533≤SDay<562	Cycle 20 – Week 79 (Cycle Day 15)	C20D15	547
505≤SDay<533	Cycle 19 - Week 75 (Cycle Day 15)	C19D15	519
477≤SDay<505	Cycle 18 – Week 71 (Cycle Day 15)	C18D15	491
449≤SDay<477	Cycle 17 - Week 67 (Cycle Day 15)	C17D15	463
421≤SDay<449	Cycle 16 – Week 63 (Cycle Day 15)	C16D15	435
393≤SDay<421	Cycle 15 – Week 59 (Cycle Day 15)	C15D15	407

Abbreviations: SDay: study day for individual participant

Table 11: Visit Windows - LTFU Phase

Assessment Study Day	Visit	Visit Label	Study Visit Day
673≤SDay<701	Cycle 25 – Week 99 (Cycle Day 15)	C25D15	687
701≤SDay<729	Cycle 26 - Week 103 (Cycle Day 15)	C26D15	715
(X³-1)*28≤SDay <x³)*28< td="">Cycle X^a = Week 4X^a-1 (Cycle Day 15)	CX^aD15	(Xa-1)*28+15	</x³)*28<>	Cycle X ^a = Week 4X ^a -1 (Cycle Day 15)	CX ^a D15	(Xa-1)*28+15
	Safety Follow-up - 30 days after last dose	LTSFU	

^aFor X>26 and a whole number Abbreviations: SDay: study day for individual participant

For tumor volume/tumor response data, the nominal visit as entered in the CRF will be used unless a visit is recorded as "Unscheduled". If an assessment is unscheduled, it will be assigned to a cycle using the windowing laid out in Table 12. If a record is mapped to a visit which has a valid reading nominally assigned, the nominally assigned visit value will be used in all summaries and analysis.

Table 12: Tumor Visit Windows

Assessment Study Day	Visit	Visit Label	Study Visit Day
2≤Sday≤182	Cycle 5	C5D15	127
182 <sday≤294< td="">Cycle 9	C9D15	239	</sday≤294<>	Cycle 9	C9D15	239
294 <sday≤406< td="">Cycle 13	C13D15	351	</sday≤406<>	Cycle 13	C13D15	351
406 <sday≤518< td="">Cycle 17	C17D15	463	</sday≤518<>	Cycle 17	C17D15	463
518 <sday≤616< td="">Cycle 21	C21D15	575	</sday≤616<>	Cycle 21	C21D15	575
616 <sday≤714< td="">Cycle 24	C24D21	665	</sday≤714<>	Cycle 24	C24D21	665
714 <sday≤826< td="">Cycle 28	C28D15	771	</sday≤826<>	Cycle 28	C28D15	771
826 <sday≤938< td="">Cycle 32	C32D15	883	</sday≤938<>	Cycle 32	C32D15	883
((XXa-2)*28)-14 <sday≤((xxa+2)*28)-14< td="">Cycle XX	CXXD15	(XXa*28)-13	</sday≤((xxa+2)*28)-14<>	Cycle XX	CXXD15	(XXa*28)-13

^aFor XX>32 and divisible by 4. Abbreviations: SDay: study day for individual participant

For PRO assessments the nominal visit will be used if it is recorded as C1D1 or is recorded in the following table. For any other case, the visit will be mapped by study day to the closest visit using the table below. If a record is mapped to a visit which has a valid reading nominally assigned, the nominally assigned visit value will be used in all summaries and analysis.

Document: S:\Q_146\Q_03974\MEK-NF-201\Prog_Stat\Documentation\SAP\MEK-NF-201 SAP v1.0.0.docx

Author:

Table 13: PRO Visit Windows

Assessment Study Day	Visit	Visit Label	Study Visit Day
2≤Sday≤99	Cycle 3	C3D15	71
99 <sday≤155< td="">Cycle 5	C5D15	127	</sday≤155<>	Cycle 5	C5D15	127
155 <sday≤211< td="">Cycle 7	C7D15	183	</sday≤211<>	Cycle 7	C7D15	183
211 <sday≤294< td="">Cycle 9	C9D15	239	</sday≤294<>	Cycle 9	C9D15	239
294 <sday≤406< td="">Cycle 13	C13D15	351	</sday≤406<>	Cycle 13	C13D15	351
406 <sday≤518< td="">Cycle 17	C17D15	463	</sday≤518<>	Cycle 17	C17D15	463
518 <sday≤616< td="">Cycle 21	C21D15	575	</sday≤616<>	Cycle 21	C21D15	575
616 <sday≤714< td="">Cycle 24	C24D21	665	</sday≤714<>	Cycle 24	C24D21	665
714 <sday≤826< td="">Cycle 28	C28D15	771	</sday≤826<>	Cycle 28	C28D15	771
826 <sday≤938< td="">Cycle 32	C32D15	883	</sday≤938<>	Cycle 32	C32D15	883
((XX ^a -2)*28)-14 <sday≤((xxa+2)*28)-14</sday≤((xx	Cycle XX	CXXD15	(XX*28)-13

^aFor XX>32 and divisible by 4. Abbreviations: SDay: study day for individual participant

For all other efficacy assessments, a similar algorithm to above will be used, with all unscheduled and ET assessments mapped to the nearest scheduled assessment visit by study day, with the earlier scheduled visit being used in the case of a tie. In the case that multiple records are recorded for a participant as the same nominal visit, the average of the results will be taken. If both unscheduled visits are equidistant from the visit being mapped to, then the earlier visit will be mapped.

The Study Visit Day of an event/assessment will be calculated relative to the first study treatment administration. The Study Visit Day of events/assessments occurring before the first administration will be calculated as follows:

Study Visit Day = (Date of assessment/event - Date of first study treatment administration).

For events/assessments occurring at baseline or post-baseline, Study Visit Day will be calculated as follows:

Study Visit Day = (Date of assessment/event - Date of first study treatment administration) + 1.

For DoR and other time-based endpoints, such as exposure, time periods may be presented in months rather than days. In these cases, the following formula will be used for conversion:

time in months = (time in days/365.25)*12.

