- 11. PK sampling will be collected throughout the study, in parallel according to the sampling schedule found in Section 10.8. The evening before each study visit (as described in the SoA), participants will record the exact time study treatment was taken in the home ePRO device. Refer to Section 8.5, Section 8.6 and central laboratory manual for more details.
 - 11a. At Cycle 1 Day 1, PK sampling is required prior to the first dose of study treatment and 1-hour post dose with an additional PK sample 2-hours post dose. Refer to Section 10.8 for sampling window requirements.
 - 11b. At Cycle 1 Day 15, serial PK sampling is required at the following timepoints: pre-dose and 0.5, 1, 2, 3 and 4-hours post dose. Refer to Section 10.8 for sampling window requirements.
 - 11c. Pre-dose PK sampling is required at select visits throughout the study as described in the SoA and Section 10.8. These blood draws will be collected prior to the morning dose of study treatment. Participants will **not** take their planned morning dose the day of the study visit. The morning dose will be taken following the pre-dose blood draw.
- 12. Tumor volume of target PN will be measured by MRI (no contrast required) and all scans will be submitted for independent, blinded central radiologic review throughout the study. If sedation is used for the MRI assessment, sedation must be administered after the strength, range of motion, and 6-minute walk assessments if assessments are to be completed on the same day.

CONFIDENTIAL Protocol MEK-NF-201

Amendment 4 (17May2022)

- 12a. MRI at Screening is required for all participants to confirm that PN is analyzable to volumetrics (determined by central radiologic review to confirm Inclusion Criterion 5) using the REiNS criteria and will serve as the participant's Baseline scan throughout the study. If applicable, scans acquired prior to the participant signing ICF may be used as Screening time point scans if they were obtained within 45 days of the first study treatment administration and the participant meets study requirements.
- **12b.** MRI at early termination (ET) visit only required if not performed within the past 3 months.

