8.1.1. Tumor Imaging

8.1.1.1. MRI Assessment

Target PN volume will be measured by MRI (no contrast required, sedation permitted per institutional policy) at the Screening visit and throughout the Treatment Phase and Long-Term Follow-Up (LTFU) Phase as described in the SoA (Section 1.3, Section 1.4). Sites will submit all MRI scans for independent, blinded centralized radiologic review of tumor volume throughout the study.

MRI at Screening is required for all participants to confirm that PN is analyzable to volumetrics (determined by central radiologic review to confirm Inclusion Criterion 5) using the REiNS criteria and will serve as the participant's Baseline scan throughout the study. If applicable, scans acquired prior to the participant signing ICF may be used as Screening time point scans if they were obtained within 45 days of the first study treatment administration, central radiologic review confirms that the target PN scan is analyzable by volumetrics using the REiNS criteria, and the participant meets study requirements. These scans will then be collected, stored, and documented as the Screening scan, and will be required to be submitted to the central radiologic review. No other pre-enrollment images will be collected or stored for the study.

Before the study is initiated at each Site, Sites will be trained on imaging requirements and guidance on how to submit scans for central radiologic review. Refer to the imaging acquisition manual and the imaging submission manual, which describe the imaging methods and submission process that Sites must follow.

The imaging protocol outlined in the imaging manual will be used each time MRI examinations are performed to assess progression or response. In participants with clinical suspicion of disease progression, MRI volumetric analysis should be performed earlier than specified in the protocol. If because of unforeseen reasons, a MRI time window is passed, but not yet at the time of the opening of the subsequent window, the MRI should be performed, and the protocol deviation noted.

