2.2 Study Design

MEK-NF-201 is a multi-center, open-label, single-arm, longitudinal, uncontrolled, Phase 2b study to evaluate the efficacy, safety, and tolerability of mirdametinib in participants ≥ 2 years of age with an inoperable NF1-associated PN that is causing significant morbidity.

This study will consist of two phases: the Treatment Phase and the optional Long-Term Follow-Up (LTFU) Phase. Approximately 100 participants will be enrolled and stratified by age (approximately 50 participants 2 to 17 years of age and 50 participants ≥ 18 years of age). The first five participants enrolled in the pediatric cohort must be 9 to 17 years of age at the time of signing informed consent/assent. After the first 5 participants have enrolled in the pediatric cohort, enrollment into this cohort will be paused, and only after Data Monitoring Committee (DMC) evaluation of at least 2 cycles of cumulative safety data for these 5 participants will the pediatric cohort be re-opened and potentially expanded down to 2 years of age. Note the adult cohort will not be affected by this special procedure; participants ≥ 18 years of age will be enrolled continuously from the outset.

Document: S:\Q_146\Q_03974\MEK-NF-201\Prog_Stat\Documentation\SAP\MEK-NF-201 SAP v1.0.0.docx

Participants will be screened for up to 45 days prior to the first dose of study treatment (mirdametinib) and eligibility will be based on the inclusion and exclusion criteria listed in Sections 5.1 and 5.2 of the protocol, respectively. Study treatment will then be administered orally at a dose of 2 mg/m² BID with a maximum dose of 4 mg BID. Dosing in the Treatment Phase will be on a 28-day cycle with a 3 week on/1 week off schedule for up to 24 Cycles. Eligible participants will take their first dose of study treatment following all pre-dose assessments on Cycle 1 Day 1. All participants will remain in the Treatment Phase of the study until radiographic disease progression (confirmed by central review), they discontinue study treatment for any other reason, the study is stopped by the sponsor for any reason, or the participant has completed the study through Cycle 24.

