Tumor volume (mL) will be assessed using MRI scans that will be taken at screening, then every 4 cycles at Cycles 5, 9, 13, 17, 21, 24, and ET for the Treatment Phase, and Cycle 28 and every 4 cycles after that, up to and including end of treatment (EOT), for the LTFU Phase, if applicable. Only tumor assessments during the Treatment Phase and prior to the first treatment start date in the long-term follow up will be considered for the determination of confirmed response. Unscheduled visits will be mapped to a visit window based on the criteria in Section 5.6.

The FAS will be used to calculate the confirmed ORR. Participants who do not have a post-baseline MRI assessment or do not achieve a confirmed response will be categorized as non-responders, and their best overall response will be deemed as "Missing".

Document: S:\Q_146\Q_03974\MEK-NF-201\Prog_Stat\Documentation\SAP\MEK-NF-201 SAP v1.0.0.docx

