4.1.3.6 Time to Progression

Time to progression (TTP) is defined as the time in months between the start of treatment to the first date of radiographic disease progression as measured by MRI. TTP will be summarized in months as follows: (date of event (i.e., radiographic disease progression) or censoring – treatment start date + 1) / 365.25 *12. Participants without radiographic disease progression will have their results censored at the last adequate tumor assessment date. Participants who lack any tumor response data post baseline will have their event time censored at treatment start date.

If participants receive any surgery impacting the target PN or start subsequent systemic therapy for the treatment of PNs prior to radiographic progression, then the participant's event time will be censored at the last adequate tumor assessment date prior to surgery or subsequent PN treatment. The rules for censoring and events for TTP are summarized in Table 6.

TTP will be analyzed for the FAS and also a subset of participants in the FAS who have progressive disease at baseline.

Table 6: Censoring and Event Rules for TTP

Situation	Date of Censoring or Event	Outcome
No adequate tumor assessment post baseline	Treatment start date	Censored

Document: S:\Q_146\Q_03974\MEK-NF-201\Prog_Stat\Documentation\SAP\MEK-NF-201 SAP v1.0.0.docx

Author:

Situation	Date of Censoring or Event	Outcome
No radiographic disease progression	Date of last adequate tumor assessment	Censored
Two or more consecutive missing or non- adequate tumor assessments	Date of last adequate tumor assessment before the first missing or non-adequate assessment	Censored
Death before radiographic progression	Date of last adequate tumor assessment	Censored
New surgery or subsequent anticancer PN therapy started prior to radiographic disease progression	Date of last adequate tumor assessment before the start of new therapy or surgery	Censored
Radiographic disease progression that has been verified by BICR	Date of the earliest tumor assessment that results in a finding of progression	Event

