4.1.3.10 Tumor Volume

Tumor volume (mL) will be measured independently by two blinded independent central reviewers, as described in Section 4.1.1. Unscheduled visits may be mapped to a visit window based on the criteria in Section 5.6.

The volume measured at the screening (SCR Volume) visit will be taken as the baseline for calculation of confirmed objective response rate, with percentage change from baseline at Cycle X (CX) calculated as:

((CX Volume - SCR Volume)/SCR Volume)*100.

The above calculation will be done for the average of the volumes recorded by each reviewer, unless there was a response adjudication in which the adjudicated reviewer's volume will be selected. In addition, this calculation will be done for each reviewer separately.

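### SAP 5.6 lets a scheduled tumour scan displace an unscheduled one, while Tables 5–7 date progression at the earliest scan showing it, and nothing ranks the two rules (minor)

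*SAP*

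**What the plan says.** **Windowing.** SAP 5.6 covers tumour volume and tumour response data. The visit entered in the CRF is used unless it is recorded as unscheduled: "If an assessment is unscheduled, it will be assigned to a cycle using the windowing laid out in Table 12". If the scan then falls in "a visit which has a valid reading nominally assigned, the nominally assigned visit value will be used in all summaries and analysis".

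**Event dates.** Table 5 (DoR), Table 6 (TTP) and Table 7 (PFS) each give the date of a progression event as "Date of the earliest tumor assessment that results in a finding of progression". Sections 4.1.2.1, 4.1.3.6 and 4.1.3.7 do not cite 5.6, and 5.6 makes no exception for time-to-event endpoints.

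**Cross-references.** SAP 4.1.1, on response, says "Unscheduled visits will be mapped to a visit window based on the criteria in Section 5.6". SAP 4.1.3.10, on volume, says "Unscheduled visits may be mapped to a visit window based on the criteria in Section 5.6".

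**Where unscheduled scans come from.** Protocol 8.1.1.1: "In participants with clinical suspicion of disease progression, MRI volumetric analysis should be performed earlier than specified in the protocol". Under SAP 2.2, participants leave the Treatment Phase at centrally confirmed progression. Footnote 12b of the protocol's Treatment Phase schedule adds: "MRI at early termination (ET) visit only required if not performed within the past 3 months".

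**Best overall response.** SAP 4.1.1 lets a single SD, PD or NE reading stand as confirmed at that level, and sets best response to Missing when the only response measurement is an unconfirmed CR or PR. Its closing paragraph then sets best response to Missing for anyone with no post-baseline MRI or no confirmed response.

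**The concern.** Two programmers following different sections could derive different TTP and PFS events from the same scans. The scans at risk under the literal 5.6 reading include those done because progression was suspected, so any error runs one way: events lost or dated late. TTP and PFS are exploratory, but SAP Table 1 names them as the endpoints to be compared with historical controls.

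The best-response wording is a separate matter. Taken literally, it empties the SD, PD and NE categories and leaves DCR, defined in SAP 4.1.3.11 as confirmed best response of SD or better, with only the confirmed responders.

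**Working it through.** **1. Scan days and windows.** Day = (cycle − 1) × 28 + 15, or + 21 for Cycle 24. This reproduces Table 12: 127, 239, 351, 463, 575, 665, 771, 883. The windows are 2–182, 183–294, 295–406, 407–518, 519–616, 617–714, 715–826 and 827–938, with no gaps. So in a participant with every scheduled scan, literal 5.6 sets aside every unscheduled scan.

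**2. One interval (Cycle 5 to Cycle 9, days 128–238).**
- Days 128–182 (55 of 111) map back to the Cycle 5 scan already done. If the Cycle 9 scan shows PD, the event is 239 − 182 = 57 to 239 − 128 = 111 days late. If there is no later scan, the event is lost.
- Days 183–238 (56 of 111) map forward. If the Cycle 9 scan is done and shows PD, the event is 1 to 56 days late. If it is not done, the unscheduled scan is kept and nothing is lost.

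**3. Worked example.** Cycle 9 scan on day 239: SD. Unscheduled scan on day 280: PD, mapped to Cycle 9 (183–294). The participant stops, and no ET MRI is needed because one has just been done.
- Table 6 or 7: event at 280/365.25 × 12 = 9.20 months.
- Literal 5.6: censored at 239/365.25 × 12 = 7.85 months.
- If the participant continued and the day-351 scan showed PD: event 351 − 280 = 71 days late.

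**4. Size, under assumptions.** The documents give no rate of unscheduled scans. A simulation of 400,000 participants assumed exponential progression, scans on the Table 12 days, and a share of progressions first seen on an unscheduled scan placed uniformly between onset and the next scheduled scan, with all affected participants stopping. Day 672 is 24 × 28, the end of Cycle 24.

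| Share first seen unscheduled | Events lost | Day-672 estimate, 85% case | Day-672 estimate, 70% case |
|---|---|---|---|
| none | – | 0.8515 | 0.7023 |
| 10% | 1.2% | 0.8531 | 0.7052 |
| 30% | 3.7% | 0.8564 | 0.7112 |
| 50% | 6.2–6.3% | 0.8596 | 0.7176 |

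The estimate rises by 0.002 to 0.008 in the 85% case and 0.003 to 0.015 in the 70% case. If all affected participants continue, the day-365 and day-672 estimates change by at most 0.0002.

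**5. DoR.** Main-analysis PD is measured from baseline, so a responder must regrow from at most 80% to at least 120% of baseline: 1.20/0.80 = 1.5. At the observational growth rates in protocol 4.2 (21.1% and 8.4% per year) that takes ln 1.5/ln 1.211 = 2.1 years and ln 1.5/ln 1.084 = 5.0 years. Growth over one 112-day interval would be 1.211^(112/365.25) − 1 = 6.0% and 1.084^(112/365.25) − 1 = 2.5%.

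**6. Why the repair should not reach ORR.** Confirmation needs a consecutive scan 2–6 months later; 2 months = 60.875 days.
- Could raise ORR: PR on day 239, unscheduled PR on day 310, SD on day 351. Under 5.6 the day-310 scan maps to Cycle 13 (295–406) and is set aside, so the response is unconfirmed. If admitted, 310 − 239 = 71 days = 2.33 months, confirmed.
- Could lower ORR: PR on days 575 and 665 (90 days, 2.96 months) is confirmed. Admit an unscheduled PR on day 620 and each consecutive gap is 45 days (1.48 months), too short; LTFU scans cannot be used.

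**7. Best response.** ORR is the same under either rule, since these participants are non-responders both ways. Each SD participant set to Missing lowers DCR by 1/50 = 2 points in a cohort of 50.

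**The case against.** The strongest reply is that 5.6 is by-visit housekeeping. The same precedence sentence is applied to safety and PRO data, whereas TTP, PFS and DoR are defined by date, and their sections never send the reader to 5.6. On the usual principle that a specific rule beats a general one, Tables 5–7 govern. A sensible programmer may well read it so, but 5.6 says all summaries and analysis, names response data, and is cited by the section that defines progression. The choice should not be left to inference.

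Several other points stand and keep this minor:
- The trigger depends on labelling. Protocol 8.1.1.1 does not say how a scan brought forward is entered; one recorded under a nominal visit or as ET is not affected.
- Losing an event requires an unscheduled label, PD first seen there, a window already holding a valid scan, and no later scan.
- The REiNS all-scans sensitivity analyses (SAP 4.1.3.6.1 and 4.1.3.7.1) and the MRI listings (SAP 6.11.1) would partly reveal a masked PD. The former are run by reader under a different progression definition, so they do not settle the main analysis.
- If the closing paragraph of 4.1.1 means confirmed in the sense used earlier in that section, the best-response conflict disappears. The text does not say so.

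A reader might infer that the plan requires progression scans to be discarded, or that TTP and PFS will be materially biased. The documents support neither: they contain two unranked rules and no count of unscheduled scans.

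**Conclusion.** The ambiguity is real and the point is minor. One literal reading of SAP 5.6 can remove or delay TTP and PFS events that Tables 6 and 7 would count, always in the favourable direction. Whether this happens depends on how sites label early scans and on whether participants stop. The sizes in the table rest on assumed progression rates, shares and scan timing, and on every affected participant stopping; they indicate scale and are not estimates for this trial.

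It would be tempting to extend the point to DoR as an equal risk, because Table 5 carries the same wording. The regrowth needed makes that unlikely in the main analysis. It would also be tempting to conclude that the primary endpoint needs every unscheduled scan counted. That does not follow, because such a change could move ORR either way.

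The Missing rule in SAP 4.1.1 is a separate minor wording conflict. It affects the best-response table and DCR only.

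**What to change.** **SAP 5.6.** Add that nominal-visit precedence does not apply to progression event and censoring dates for DoR, TTP and PFS, which use every evaluable BICR scan at its actual date, scheduled or not. Leave the derivation of confirmed ORR and best response unchanged, including the handling of unscheduled scans and the 2–6 month confirmation rule.

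**SAP 4.1.1, closing paragraph.** Keep the non-responder rule for ORR. Limit Missing to participants with no post-baseline MRI assessment, or whose only post-baseline readings are unconfirmed CR or PR (one or more). The plural matters: PRs on days 127 and 351 with Cycle 9 missed are 224 days (7.36 months) apart, so neither confirms the other, and the participant still needs a category. SD, PD and NE participants then keep theirs.

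**Cost.** Two short text changes and minor programming. TTP and PFS may look slightly less favourable. Because best response is left alone, a participant with PD on a displaced unscheduled scan and a later scheduled response would have a TTP event and still count as a responder. That needs a fall from at least 120% to at most 80% of baseline (1 − 0.80/1.20 = 33%), so it should be rare. ORR is unaffected by either change.
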